6.2.2 Secondary Variable(s)

Secondary variables include:

Efficacy:

- Body weight (change from Baseline)
- Body length (change from Baseline)
- Head circumference (change from Baseline)
- Time to full enteral or oral feeds
- Fatty acids in plasma and red blood cell membranes (change from Baseline)
- Holman index

Safety:

- Length of stay in hospital
- Ratio of number of independent bloodstream infections / number of days on study medication
- Ratio of the number of patients with 1 or more bloodstream infections / number of patients on study medication
- Number of patients who complete PN treatment without lipid minimization
- Number of patients who need to be withdrawn from the study due to elevated conjugated bilirubin levels
- Area under the curve of conjugated bilirubin for time period in which levels are > 1.5 mg/dL
- Cumulative number of days patients are administered a lipid dose without lipid minimization
- Time to conjugated bilirubin > 2 mg/dL (confirmed by a second sample collected 7 days after the first)
- Conjugated bilirubin
- Total bilirubin
- Serum TGs
- Aspartate aminotransferase (AST)
- Alanine aminotransferase (ALT)
- Gamma-glutamyl transferase (GGT)
- Alkaline phosphatase (ALP)
- Blood glucose
- Blood urea nitrogen (BUN)
- Creatinine
- C-reactive protein (CRP)
- Sterols including phytosterols
- α -tocopherol
- Collection of AE data
- Incidence of bronchopulmonary dysplasia (BPD)
- Incidence of retinopathy of prematurity (ROP)
- Incidence of intraventricular hemorrhage (IVH)

Clinical Study Protocol SMOF-018-CP3 **Smoflipid 20% lipid injectable emulsion**

- Incidence of periventricular leukomalacia (PVL)
- Incidence of necrotizing enterocolitis (NEC)
- Incidence of late-onset sepsis in premature and low birth weight neonates

7 Study Design

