8.2 Statistics

8.2.1 Study Outcome Measures

The primary outcome measure is the number of patients in each treatment group with conjugated bilirubin > 2 mg/dL during the first 28 days of study treatment, confirmed by analysis of a second sample collected 7 days after the first sample.

The secondary outcome measures are:

Efficacy:

- Body weight (change from Baseline)
- Body length (change from Baseline)
- Head circumference (change from Baseline)
- Time to full enteral or oral feeds
- Fatty acids in plasma and red blood cell membranes (change from Baseline)
- Holman index

Safety:

- Length of stay in hospital
- Ratio of number of independent bloodstream infections / number of days on study medication
- Ratio of number of patients with 1 or more bloodstream infections / number of patients who received study medication
- Number of patients who complete the PN treatment without lipid minimization
- Number of patients who need to be withdrawn from the study due to elevated conjugated bilirubin levels
- Area under the curve of conjugated bilirubin for time period in which levels are > 1.5 mg/dL
- Cumulative number of days patients are administered a lipid dose without lipid minimization
- Time to conjugated bilirubin > 2 mg/dL (confirmed by a second sample collected 7 days after the first)
- Conjugated bilirubin
- Total bilirubin
- Serum TGs
- AST
- ALT
- GGT

Clinical Study Protocol SMOF-018-CP3

Smoflipid 20% lipid injectable emulsion

- ALP
- Blood glucose
- BUN
- Creatinine
- CRP
- Sterols including phytosterols
- α -tocopherol
- Collection of AE data
- Incidence of Bronchopulmonary Dysplasia (BPD)
- Incidence of Retinopathy of Prematurity (ROP)
- Incidence of Intraventricular hemorrhage (IVH)
- Incidence of Periventricular Leukomalacia (PVL)
- Incidence of Necrotizing Enterocolitis (NEC)

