5.2 Secondary Variables

5.2.1 *Efficacy Variable*

- Body weight (age-standardized*)
- Body length (age-standardized*)
- Head circumference (age-standardized*)
- Time to full enteral or oral feeds
- Fatty acids in plasma and red blood cell membranes
- Holman index

* Anthropometric data (weight, length, and head circumference) will be standardized by age and gender according to the WHO and Fenton standards.

5.2.2 *Safety Variables*

- Adverse events (AEs)
- Length of stay in hospital (Time to discharge from hospital)
- Ratio of number of independent bloodstream infections / number of days on study medication
- Ratio of the number of patients with 1 or more bloodstream infections / number of patients on study medication
- Completion of PN treatment without lipid minimization (Yes or No)
- Withdrawal from the study due to elevated conjugated bilirubin levels (Yes or No)
- Area under the curve (AUC) of conjugated bilirubin for time periods in which levels are > 1.5 mg/dL
- Cumulative number of days of PN without lipid minimization
- Number of days until conjugated bilirubin > 2 mg/dL confirmed by a second sample collected 7 days after the first sample
- Conjugated bilirubin

Statistical Analysis Plan

FK Study Identifier: SMOF-018-CP3

- Total bilirubin
- Serum triglycerides (TGs)
- Aspartate aminotransferase (AST)
- Alanine aminotransferase (ALT)
- Gamma-glutamyl transferase (GGT)
- Alkaline phosphatase (ALP)
- Blood glucose
- Blood urea nitrogen (BUN)
- Creatinine
- C-reactive protein (CRP)
- Sterols including Phytosterols
- α -tocopherol

Statistical Analysis Plan

FK Study Identifier: SMOF-018-CP3

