7 STATISTICAL CONSIDERATIONS AND DEFINITIONS

All data will be evaluated descriptively and in an exploratory way. Point estimates of differences between treatment groups and corresponding two-sided 95%-confidence intervals will be presented for the primary and key secondary efficacy endpoints. Statistical hypotheses will not be tested and p-values will not be reported.

The analysis of the primary and secondary efficacy endpoints will be performed using both the ITT analysis set and the per protocol set. The analysis of the secondary safety endpoints will be performed using the safety set.

Descriptive statistics will be displayed to provide an overview of the efficacy and safety results by treatment group, stratum and overall. For categorical parameters, these will consist of the number and percentage of patients in each category. The denominator for percentages will be based on the number of patients in the corresponding analysis set, missing will be displayed as a category. For continuous parameters, descriptive statistics will include number of patients with number of non-missing values, mean, standard deviation, median, minimum, and maximum.

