Annex No.: **[REDACTED]**
Document No.: **[REDACTED]**

00

1

Date:

Page:

[REDACTED]
36 of 56

Statistical Analysis Plan

FK Study Identifier: SMOF-018-CP3

Categorization of Z-Scores on Fenton and WHO Growth Charts

Z-score cut-off	Category	Corresponding p%-percentile
$Z \leq -1.88$	Low for age	$p \leq 3\%$
$-1.88 < z < 1.88$	Normal	$3\% < p < 97\%$
$Z \geq 1.88$	High for age	$p \geq 97\%$

Categorization of age-standardized Z-score will be performed for the end of the initial treatment phase and the end of the extended treatment phase. The number and percentage of patients with low, normal and high weight for age will be presented by time point (including end of treatment and end of study) and treatment group.

Anthropometric data will be listed and summarized by time point and treatment group, and Spaghetti plots and box plots over time will be displayed by treatment group.

Patient listings of measured anthropometric data (body weight [g], height/length [cm], head circumference [cm], corresponding Z-scores after standardization for age, and allocated categories will be provided.

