8.11.3 Fatty Acids in Plasma and Red Blood Cell Membranes

Fatty acids to be assessed include linoleic acid, α -linolenic acid, Mead acid, eicosapentaenoic acid, arachidonic acid, docosahexaenoic acid. The fatty acids and absolute and relative change from baseline will be summarized descriptively by underlying disease group and treatment group.

The incidence of essential fatty acid deficiency and shift from baseline will be summarized with descriptive statistics by treatment group. Essential fatty acid deficiency is based on the ratio of Mead acid and Arachidonic acid (also called the triene/tetraene ratio or Holman index; Holman, 1960). A ratio of > 0.2 will be considered abnormal (=essential fatty acid deficiency; Holman et al., 1979). The Holman index (= triene/tetraene ratio) will be calculated by statistical programming.

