8.12.5 Clinical Laboratory

Laboratory assessments and change from baseline will be summarized with descriptive statistics by test panel, individual laboratory test, underlying disease and group treatment group, and time point. Additionally, abnormal results including normal, abnormal clinically significant (abnormal CS), abnormal not clinically significant (abnormal NCS) captured by the eCRF will be summarized with

Statistical Analysis Plan

FK Study Identifier: SMOF-018-CP3

frequencies and percentages by clinical significance, panel, test, underlying disease group and treatment group, and time point. The denominators for percentages will be the number of patients in the analysis set for the treatment group summarized. Missing values will be presented in the summary tables. Counts and percentages of patients with shifts for the period from baseline to the end of the initial treatment phase will be summarized by analyte, underlying disease group and treatment group:

- Normal -> abnormal CS: from normal at Baseline (Day 0 or Day 1) to abnormal CS at the end of the initial treatment phase
- Normal -> abnormal NCS: from normal at Baseline to abnormal NCS at the end of the initial treatment phase
- Abnormal NCS -> abnormal CS: from abnormal NCS at Baseline to abnormal CS at the end of the initial treatment phase
- In addition, counts and percentages of patients with shifts for the period from baseline to the end of the extended treatment phase will be summarized by analyte and treatment group as described above. In this table, the denominator will be number of patients still in the study at the end of the initial treatment phase.

A data listing will display all laboratory test results and findings. A listing of lab data (including all visits) for patients who had at least one abnormal result will be provided.

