8.12.6 Vital Signs

Vital sign measurements and change from baseline of vital signs (including heart rate, temperature, systolic and diastolic blood pressure) will be summarized with descriptive statistics by underlying disease group, treatment group, and time point. A data listing of all data will also be included.

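### SAP 8.11.1 drops the protocol's change from baseline for weight, length and head circumference, and no planned growth comparison between arms uses the baseline values

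*SAP*

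**What the plan says.** The protocol lists the three growth measures as changes, in its synopsis, in Section 6.2.2 ("Body weight (change from Baseline") and in Section 8.2.1 ("Head circumference (change from Baseline"); body length is treated the same way. They are three of six secondary efficacy variables. The others are time to full feeds, fatty acids and the Holman index.

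SAP 5.2.1 lists the same variables without the change, for example "Body weight (age-standardized". SAP 8.11.1 converts the measurements to Fenton or WHO Z-scores and assigns low, normal or high categories at the end of each treatment phase. It then states: "Anthropometric data will be listed and summarized by time point and treatment group, and Spaghetti plots and box plots over time will be displayed". It mentions no change or shift from baseline and no between-arm estimate.

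Elsewhere the same SAP keeps the change:
- Section 8.11.3: "The fatty acids and absolute and relative change from baseline will be summarized descriptively by underlying disease group and treatment group"
- Section 8.12.5: "Laboratory assessments and change from baseline will be summarized with descriptive statistics"
- Section 8.12.6: "Vital sign measurements and change from baseline of vital signs"

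On estimates, SAP Section 7 says: "Point estimates of differences between treatment groups and corresponding two-sided 95%-confidence intervals will be presented for the primary and key secondary efficacy endpoints". It does not say which secondary endpoints are key.

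**The concern.** Age standardisation changes the scale of measurement. It does not replace the within-infant change that the protocol made the endpoint; change in Z-score would satisfy both documents. A Z-score corrects for age and sex but not for where each infant started. If one arm happens to begin smaller for age, a visit-by-visit reading carries part of that difference into the end-of-phase comparison.

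A reader cannot repair this from the planned tables. Study drug stops when enteral feeding is established, and an End-of-Treatment Visit follows the next day (Protocol 7.1 and 11.3), so different infants may contribute at Day 1 and at later visits. Subtracting two visit means then does not give the mean within-infant change, and its SD or CI cannot be recovered from summaries by visit. The protocol makes nutritional efficacy a secondary objective and names growth in its stated purpose (Section 5.2).

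**Working it through.** **Text comparison**

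| Variable | Protocol | SAP |
|---|---|---|
| Weight, length, head circumference | Change from baseline | Values and Z-scores by visit and arm; categories at end of phase |
| Fatty acids | Change from baseline | Values plus absolute and relative change |
| Laboratory values | No change specified in the variable list | Values plus change |
| Vital signs | Not in the variable list | Values plus change |

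The change can be derived. SAP 7.9 defines baseline for efficacy variables, and Protocol 12.2.2 has weight, length and head circumference measured on Day 1. Baseline size enters the SAP as a baseline characteristic (8.3), and may appear as the Day 1 point in summaries and plots, but in no comparison. The only covariate provision (7.6) is stratification of the primary endpoint. In the SAP's change log (2.2), the only analysis entry specific to growth is the replacement of a line plot by a box plot.

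**Size**

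The plan states no figure to reproduce. The calculation below is an illustration.

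Inputs:
- n = 76 per arm: 152 randomised at the interim (SAP 8.8), split evenly (assumed).
- SD = 1 Z at baseline and at end of phase (assumed).
- Baseline-to-end correlation ρ = 0.3 to 0.9 (assumed; not in the documents).

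Formulas:
- SE of the unadjusted difference = √(2/76) = 0.162; 95% half-width = 1.96 × 0.162 = 0.318 Z.
- Baseline-adjusted: variance × (1 − ρ²), half-width 0.318 × √(1 − ρ²).
- Change score: variance × 2(1 − ρ), half-width 0.318 × √(2(1 − ρ)).
- Carry-over of a baseline imbalance d into the unadjusted comparison = ρ × d.

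| ρ | Adjusted variance ratio | Adjusted half-width | Change-score variance ratio | Change-score half-width | Carry-over, d = 0.162 | Carry-over, d = 0.3 |
|---|---|---|---|---|---|---|
| 0.3 | 0.91 | 0.303 | 1.4 | 0.376 | 0.049 | 0.09 |
| 0.5 | 0.75 | 0.275 | 1.0 | 0.318 | 0.081 | 0.15 |
| 0.7 | 0.51 | 0.227 | 0.6 | 0.246 | 0.114 | 0.21 |
| 0.8 | 0.36 | 0.191 | 0.4 | 0.201 | 0.130 | 0.24 |
| 0.9 | 0.19 | 0.139 | 0.2 | 0.142 | 0.146 | 0.27 |

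An imbalance of 0.162 Z is one SE. An imbalance of 0.3 Z is 0.3/0.162 = 1.85 SE, with two-sided probability 0.064. The adjusted estimate is at least as precise as either alternative throughout this range. The change score gains precision over the unadjusted comparison only above ρ = 0.5.

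**The case against.** The best case against the point accepts the wording gap and disputes its weight.

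- **Descriptive analysis was foreseen.** Protocol 8.2.7 limits secondary outcomes to descriptive statistics if the trial stops after the interim because the required sample is infeasible, and neither document ever planned a baseline-adjusted growth model. The second part is true, so the model is an addition to the plan. But a tabulated change needs no test, and the SAP already reports Fine and Gray hazard ratios with CIs (8.11.2).
- **The gains shown belong to the adjusted model.** Correct: restoring the protocol's change score alone would lose precision at ρ = 0.3 and gain none at 0.5. That is why the model is proposed beside the change table.
- **Carry-over and CI width are one effect.** This stands. Under randomisation the unadjusted difference is unbiased, and ρ × d is the part of its sampling error that baseline explains. The two sets of figures must not be added together or read as bias beyond the unadjusted CI.
- **The inputs are assumed.** Apart from 152, they are. Moreover, 152 is neither the final number, since a few more infants enrolled in stage 2, nor the number with a Day 29 value.
- **The outputs are unseen.** The table shells are separate, and the fatty-acid table titles omit the change that 8.11.3 plans, so titles prove nothing. The finding rests on the text of 5.2.1 and 8.11.1.
- **The SAP may change methods.** Protocol 8.2.3 allows this if it is documented. Age standardisation is stated openly; the loss of the change is not explained anywhere. The log covers only major changes since SAP version 1.0, so the omission may be older.

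**Conclusion.** The concern holds. On the SAP's text, three protocol-defined endpoints lose their change from baseline without a stated reason, and no planned between-arm growth comparison uses baseline. Baseline data are collected, tabulated and listed; the gap lies in the comparison.

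Confidence in the mismatch is high. Its numerical size is only illustrative: under the stated assumptions, adjustment removes 9% to 81% of the variance of the arm difference, depending on ρ. The change should be made because it restores a defined endpoint and sharpens the growth results at almost no cost. The undefined term for key secondary endpoints in Section 7 leaves it unclear whether growth gets any estimate, but that is a matter of missing detail and the conclusion does not depend on it.

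**What to change.** In SAP 8.11.1:

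1. Tabulate change in Z-score from baseline by visit and arm for weight, length and head circumference.
2. Report the between-arm difference in Z-score at the end of the initial phase (Day 29, or an earlier End-of-Treatment value) with a 95% CI, labelled exploratory and without a p-value. Take it from a linear model with baseline Z-score, treatment and NEC stratum, in the ITT and per protocol sets.
3. State how many infants contribute and how early weaning, withdrawal and death are handled. An earlier End-of-Treatment value mixes treatment durations, and weaning time may itself differ by arm, so repeat the analysis with Day 29 values only as a sensitivity analysis.

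In Section 7, name the key secondary efficacy endpoints. If the sponsor prefers not to restore the change from baseline, the SAP should say so and give the reason.

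The cost is SAP wording, one added column, six model fits (three measures × two analysis sets) and a short rule for infants without a Day 29 value. No new data are needed.

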8.11.2 Time to Full Enteral or Oral Feeds

Time to full enteral or oral feeds (i.e. PN weaning) is the time from the randomization date to the date of the first full enteral or oral feeds. Patients alive who were not weaned from PN will be censored at the last follow up date (either in the initial treatment phase or in the treatment extension phase) and patients who died will be considered a competing risk. The cumulative incidence function for time to full enteral or oral feeds will be estimated using the non-parametric Aalen estimator (Aalen, 1978) and displayed graphically over time by treatment group.

The cause-specific hazard will be estimated using the subdistribution hazard model according to Fine and Gray with factors treatment, underlying disease group (No NEC /NEC) and the interaction term (Fine & Gray, 1999).

The number of patients with full enteral or oral feeds, the number of patients who died, the number of patients censored, the median time to event determined from the cumulative incidence functions

Statistical Analysis Plan

FK Study Identifier: SMOF-018-CP3

by underlying disease group and treatment group and the hazard ratio and its 95% confidence interval determined from the Fine and Gray-model will be presented in summary table.

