8.12.1.1 Time to discharge from hospital

Length of stay in hospital (time from randomization to discharge) will be calculated using the Worksheet of the Vermont Oxford Network (see Annex 6 to the protocol). Death during hospitalization will be considered a competing risk. Patients alive who are not reported to be discharged during the study will be censored at the last follow-up date.

The cumulative incidence function for time to discharge from hospital will be estimated using the Aalen estimator (Aalen, 1978). The cause-specific hazard will be estimated using the subdistribution hazard model according to Fine and Gray with factors treatment, underlying disease group (No NEC / NEC) and the interaction term (Fine & Gray, 1999).

Statistical Analysis Plan

FK Study Identifier: SMOF-018-CP3

The number of patients discharged from hospital, the number of patients who died, the number of patients censored, the median time to discharge from hospital determined from the cumulative incidence function and the hazard ratio and its 95% confidence interval estimated determined from the Fine and Gray-model will be presented in a summary table.

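### The SAP names the cause-specific hazard as its target in three time-to-event analyses but fits a Fine and Gray model, so the reported hazard ratios could be misread

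*SAP*

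**What the plan says.** Three SAP sections plan a competing-risk analysis: 8.11.2 (time to full enteral or oral feeds), 8.12.1.1 (time to discharge) and 8.12.1.2 (days to confirmed conjugated bilirubin > 2 mg/dL). They share one structure.

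- **Competing event.** Death. In 8.11.2: "patients who died will be considered a competing risk". In 8.12.1.1, and in the same words in 8.12.1.2: "Death during hospitalization will be considered a competing risk".
- **Curves.** In 8.11.2: "The cumulative incidence function for time to full enteral or oral feeds will be estimated using the non-parametric Aalen estimator". The other two sections also use the Aalen estimator.
- **Model.** In 8.11.2: "The cause-specific hazard will be estimated using the subdistribution hazard model according to Fine and Gray with factors treatment". In 8.12.1.1, and again in 8.12.1.2: "The cause-specific hazard will be estimated using the subdistribution hazard model according to Fine and Gray with factors treatment, underlying disease group". The third term in each model is the treatment-by-disease interaction.
- **Reported effect.** In 8.11.2: "the hazard ratio and its 95% confidence interval determined from the Fine and Gray-model will be presented in summary table". In 8.12.1.1 and 8.12.1.2: "the hazard ratio and its 95% confidence interval estimated determined from the Fine and Gray-model will be presented in a summary table".

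The results go to Tables 14.2.2.3.1 and 14.2.2.3.2 (feeds, ITT and per protocol), 14.3.7.1 (discharge) and 14.3.7.2 (bilirubin). None of the three sections specifies a Cox model with deaths censored. SAP sections 4.5 and 7 make the whole analysis descriptive, without p-values.

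**The concern.** The model sentence names one quantity as the target and the model for another.

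The cause-specific hazard is the event rate among infants who are still alive and event-free. It comes from a Cox model in which deaths are censored. The Fine and Gray model keeps infants who have died in the risk set. Its ratio therefore describes the cumulative incidence of the event and reflects the effect of treatment on death as well as on the event.

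If one arm has more deaths, its Fine and Gray ratio falls even when surviving infants reach full feeds, go home or become cholestatic at the same rate. Read as cause-specific, that fall would suggest slower feeding or discharge. For bilirubin it would suggest less cholestasis, so excess deaths could look like a safety benefit. With no p-values planned, estimates and intervals are the comparative output, so it matters that they are named correctly.

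**Working it through.** **1. Is it a contradiction or loose wording?** Setting the three sections side by side, each names the cause-specific hazard as the target, the subdistribution model as the method, and the Fine and Gray model as the source of the printed ratio. No other model is specified that could supply a cause-specific ratio. The mismatch is in the text.

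**2. How far apart can the two ratios be?** The SAP gives no hazard ratio, event rate or death rate for these analyses, so there is no figure to reproduce. What follows is an illustration.

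Inputs:
- Horizon of 84 days: the last possible day of study drug (Protocol 12.2.5).
- Feeding hazard λ₁ = 0.03/day in the control arm: assumed.
- Death hazard λ₂ = 0.001/day in the control arm, multiplied by 1, 2, 4 or 6 in the other arm: assumed.

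Formulas for constant hazards, with s = λ₁ + λ₂:
- Event incidence: F₁(t) = (λ₁/s)(1 − e^(−st)). Death incidence: F₂(t) = (λ₂/s)(1 − e^(−st)).
- The cause-specific ratio is λ₁B/λ₁A.
- The Fine and Gray ratio θ solves ∫[f_B − (f_A + f_B)·θR_B/(R_A + θR_B)]dt = 0 over 0 to 84 days, with f = λ₁e^(−st) and R = 1 − F₁. Those who died stay in R.

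Control deaths: (0.001/0.031)(1 − e^(−2.604)) = 0.030. With a fourfold death hazard: (0.004/0.034)(1 − e^(−2.856)) = 0.111.

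| Feeding hazard, A v B (per day) | Deaths by Day 84, A v B | Cause-specific ratio | Fine and Gray ratio |
|---|---|---|---|
| 0.030 v 0.030 | 3% v 3% | 1.00 | 1.00 |
| 0.030 v 0.030 | 3% v 6% | 1.00 | 0.95 |
| 0.030 v 0.030 | 3% v 11% | 1.00 | 0.87 |
| 0.030 v 0.030 | 3% v 16% | 1.00 | 0.80 |
| 0.030 v 0.033 | 3% v 3% | 1.10 | 1.09 |
| 0.030 v 0.033 | 3% v 5% | 1.10 | 1.04 |
| 0.030 v 0.033 | 3% v 15% | 1.10 | 0.87 |

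Simulation with 200,000 infants per arm agrees to within about 0.005. For 3% v 6% it gives 0.955, against 0.951 from the integral.

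**3. When does the direction reverse?** A second setting uses 91 days and an assumed 75% control feeding incidence. With 10% control deaths and a doubled death hazard, a cause-specific ratio of 1.05 becomes 0.93 and 1.10 becomes 0.97, while 1.20 stays above 1 at about 1.05. With 3% control deaths and a doubled death hazard, 1.05 becomes 1.01 and 1.10 becomes 1.06, so there is no reversal.

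**4. Does the size carry over to bilirubin?** Only in part, because a less frequent event is less affected. With an assumed 30% incidence over 84 days and a cause-specific ratio of 1.00, the Fine and Gray ratio is 0.98 at 3% v 6% deaths and 0.95 at 3% v 11%. Discharge was not calculated separately.

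**The case against.** The best defence is that this is one wrong phrase used three times. Each section attributes the printed ratio to the Fine and Gray model and cites its paper, and the table titles do not say 'cause-specific'. The Aalen cumulative incidence curves belong to the same framework as the subdistribution hazard. Each summary table shows the number of deaths beside the events, and Tables 14.3.2.5a and 14.3.2.5b report fatal events by arm. A death imbalance large enough to move the ratio would be visible. The analyses are exploratory, and Protocol 8.2.7 says that results from such models are to be interpreted only in that way.

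Most of this stands, and it limits the consequence: a careful reader can work out what was fitted. It does not remove the contradiction, because the same paragraph tells that reader the target is cause-specific.

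A reader might infer more than the documents support:

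- *That the ratios are likely to point the wrong way.* The clear reversals at 3% control deaths rest on an assumed four- to six-fold death hazard, for which the documents give no basis. Exclusion of infants unlikely to survive 28 days (Protocol 10.3) does not establish low mortality, but nothing suggests an imbalance of that order.
- *That these are the only comparisons with an interval.* For bilirubin, SAP 8.10 already gives a stratified relative risk with 95% CI for a confirmed value > 2 mg/dL in the first 28 days.
- *That Fine and Gray is the wrong model.* It is a legitimate companion to cumulative incidence curves. The fault is in what the SAP says it estimates.

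**Conclusion.** The point holds as a mislabelled estimand in SAP 8.11.2, 8.12.1.1 and 8.12.1.2. As written, the hazard ratios for feeds, discharge and bilirubin could be read as cause-specific when they are subdistribution ratios.

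The practical size is unknown because the documents give no mortality. Under the stated assumptions for feeding it is negligible with equal deaths, about 4% to 5% with a doubled death hazard at 3% control deaths, and 13% at 3% v 11%. It is smaller for a less frequent event such as bilirubin. Reversal is possible, but only with a cause-specific ratio near 1 or a large death imbalance. The primary analysis is untouched. The SAP should still be corrected, because these are reported effect measures and the correction is cheap.

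**What to change.** - **Needed.** In SAP 8.11.2, 8.12.1.1 and 8.12.1.2, replace 'cause-specific hazard' with 'subdistribution hazard'. In Tables 14.2.2.3.1, 14.2.2.3.2, 14.3.7.1 and 14.3.7.2, label the estimate 'subdistribution hazard ratio', to be read with the cumulative incidence curves and the death counts. The cost is wording only.
- **If the cause-specific effect is what is wanted, as the text says.** Add two Cox models per endpoint, one for the event with deaths censored and one for death with the event censored, and report both ratios beside the subdistribution ratio. Together they show whether a difference comes from the event or from mortality. The cost is two simple extra models per endpoint on data already collected.
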